7.1.5. Treatment Condition

Gepotidacin 2×3000 mg versus Ceftriaxone 500 mg plus azithromycin 1 g, regardless of adherence.

7.1.6. Statistical Analyses / Methods

7.1.6.1. Statistical Methodology Specification

The primary efficacy endpoint is culture-confirmed bacterial eradication (microbiological success) of NG from the urogenital body site at the TOC visit.

Microbiological success rate and Exact Clopper-Pearson confidence interval (CI) in each treatment group will be calculated. For the statistical analysis, three strata (subgroups) will be formed according to the combinations of levels of the sex and sexual orientation (MSM, MSW, Female) at baseline. For age strata, due to few participants in <18 years and >65 years age categories, the categories <18 years, ≥18 to 65 years and >65 years will be combined for primary statistical analysis, thereby removing the age effect from the analysis. If a participant is mis-stratified, then the actual pooled strata collected in the eCRF will be used in the analysis instead of the randomized pooled strata, unless specified. The effect of this stratification is to provide statistical control over these potentially important prognostic variables.

The adjusted estimates of the difference in microbiological success rate for the two treatment groups (gepotidacin – ceftriaxone plus azithromycin) will be calculated and summarized with 2-sided 95% CI based on a stratified analysis using Miettinen and Nurminen (MN) method.

The Miettinen-Nurminen (score) confidence limits for the treatment difference [Miettinen, 1985] are computed (SAS PROC FREQ [SAS, 2018] uses iterative computation for this). Stratum based point estimates and variances can be estimated from

these CIs. The MN estimate of the common risk difference and variance is computed by combining the point estimates and variances from the individual pooled strata using MN weights. The estimate uses inverse variance stratum weights to produce MN confidence limits for the stratum risk differences. The mathematics and algorithm of MN method can be found in the SAS procedure guide under “Summary Score Estimate of the Common Risk Difference” [SAS, 2018].

This MN method is the primary estimator of the primary efficacy endpoint and will statistically test the null hypothesis contained in Section 2.4. Gepotidacin will be declared noninferior to treatment with ceftriaxone plus azithromycin if the lower limit of the 2-sided 95% confidence interval (CI) for the difference between the microbiological success rate of gepotidacin and ceftriaxone plus azithromycin at the TOC visit is above -10.0%. Superiority of gepotidacin will be declared if the lower end of the 2-sided 95% CI is above 0%. Testing for superiority using 2.5% level of significance will occur if noninferiority is achieved and one-sided p-value will be calculated.

The number and percentage of participants with culture-confirmed bacterial eradication of NG from the body site will be summarized at the TOC visit by treatment group along with the 95% Exact (Clopper-Pearson) CIs.

Microbiological response and microbiological outcome (success, failure, and reason for failure) of NG at the TOC visit will be summarized. Additional summaries providing further granularity into reasons for microbiological failure, including summaries of participants whose microbiological outcome was unable to determine, and further details on use of systemic antibiotics prior to assessments, differentiating use for the disease under study or for other conditions, may be provided.

Supportive analyses will be performed to enable the assessment of the homogeneity of the treatment difference across analysis strata used in the primary analysis.

The weighted least squares chi-squared statistic of [Fleiss, 1981] will be used to test for one-way homogeneity of the treatment difference across the levels of the strata used for the primary analysis. The overall test for homogeneity will use the combined pooled strata levels. Additional tests for homogeneity of the treatment difference across the levels of each pooled strata will be performed, with each pooled strata considered separately. Following Lui and Kelly [Lui, 2000], $\frac{1}{2}$ will be added to each cell in any stratum (pooled) for which the stratum-specific success rate estimates of either gepotidacin or ceftriaxone plus azithromycin are zero or one, and tests will be one-sided. Tests of homogeneity will be assessed at the one-sided 10% level of significance.

For each stratum, the percent of participants with microbiological successes by treatment group and unadjusted difference in percent between treatment groups with corresponding two-sided 95% CI using MN method will be reported. In addition, the *p*-value from the overall test of homogeneity will be reported.

7.1.6.2. Sensitivity Analyses

Sensitivity analyses will be performed to investigate the robustness of the primary efficacy results for the primary estimand. Treatment group differences will be displayed for subgroups with ≥ 10 participants across both treatment groups, see Section 5.4.2 for

definition of subgroups. The following sensitivity analyses will be performed in the Micro-ITT Population at the TOC visit.

- 1) An analysis of microbiological response at TOC unadjusted for the stratification factors. Unadjusted difference in proportions between treatment groups (gepotidacin – ceftriaxone plus azithromycin), and corresponding two-sided 95% CI using MN method (adjusting for treatment only) will be presented.
- 2) An analysis of microbiological response at TOC adjusted for the stratification factors based on the randomization stratum the participant was randomized to (instead of the actual stratum the participant should be assigned to). Difference in the proportion of microbiological responders between each treatment group adjusted by MN weights (using randomized stratification) will be presented along with two-sided 95% CIs (using MN method adjusting for treatment and pooled strata as randomized).
- 3) A sensitivity estimator for the primary estimand will be determined by dealing with missing values of the microbiological response at TOC per the following:
 - If the entire visit, bacteriology samples were missed due to COVID-19 then the missing value will be assessed using multiple imputation under a missing at random assumption
 - If the bacteriology sample was taken but a result is not available for the sample for any reason, then the missed value will be assessed using multiple imputation under a missing at random assumption
 - All other missing data will be assumed to be a failure

The rationale for this strategy is that it may be reasonable to assume that missing data due to either COVID-19 or due to microbiology samples which were taken but not able to be processed will not have been impacted by the treatment the patient received or their response to treatment. Microbiology samples may be missing for reasons due to COVID-19 (e.g., out of stability samples arriving at the local lab due to extended shipping times or lack of couriers to pick up the samples within agreed timeframes). But they may also be missing, for example, due to sample packing or mis-labelling issues at the site. In all cases a missing at random multiple imputation will be performed irrespective of the reason the sample is missing. All other missing data will be considered as a failure (i.e., non-responders), consistent with the primary analysis. Multiple imputations will be implemented with the following steps:

Step 1: Microbiological response will be imputed by multiple imputation using logistic regression models under a missing at random assumption in the Micro-ITT population. The number of imputations will be 1,000 and SEED= 116577. The variables used in the imputation model will include:

- Sex and sexual orientation (MSM, MSW, or female)
- Randomized Treatment group
- Interaction term between treatment and MIC (gepotidacin or ceftriaxone plus azithromycin) for randomized treatment. If needed, this may be refined prior to unblinding. Note: Baseline pathogen (*N. gonorrhoeae*)

isolate) will be determined by GSK Microbiology prior to unblinding and will include separate holistic reviews to:

- identify dominant isolate for participants with more than one *N. gonorrhoeae* isolate at Baseline. This selection will be completed for all participants with more than one *N. gonorrhoeae* isolate at Baseline in the micro-ITT Population, regardless of missing data and will be based on gepotidacin or ceftriaxone and azithromycin MIC value (and phenotypic profile if required) and will identify the dominant *N. gonorrhoeae* isolate for gepotidacin and for ceftriaxone/azithromycin treatment groups as these may differ. This will be documented prior to unblinding. Post unblinding, the dominant *N. gonorrhoeae* isolate for the randomized treatment will be used and the corresponding Baseline *N. gonorrhoeae* MICs will be used in the analysis.
- Group MICs (gepotidacin or ceftriaxone and/or azithromycin) by randomized treatment which may be based on Baseline *N. gonorrhoeae* isolate. This will be documented prior to unblinding.
- Site (Sites with <10 participants in the Micro-ITT Population may be combined prior to unblinding)

Any subjects that have a missing value for one or more variables listed above will be excluded from the relevant imputation model(s). While logistic regression will be used for the imputation model, the stratified MN statistic will be used for the analysis of each imputed dataset.

Step 2: Step 1 will produce 1,000 imputed datasets with complete data. For each dataset, participants microbiological response will then be derived using the imputed and non-missing data per Section 7.1.1. We will estimate the proportion of success in each treatment group and its standard error using the sample estimates, and the difference in the proportion of success between the two treatment groups and its standard error using the MN method weighted on actual pooled strata as in the primary efficacy analysis for each imputed dataset separately. All estimated quantities (proportion of success in each treatment group, difference between two groups, and their associated standard errors) will be saved for step 3.

Note: the number of imputations may be increased if required following model checking to ensure results are not sensitive to the random number seed and/or number of imputations.

Step 3: The estimated quantities in Step 2 will be combined across the imputed datasets using Rubin's rules to provide pooled estimates for the success rate in each treatment group and for the difference in the proportion of successes between the two treatment groups. The 95% (Wald) CIs will be calculated for the proportions of successes in each arm as well as for the risk difference between the two treatment groups. Testing for superiority may occur if noninferiority is achieved. A one-sided *p*-value will be calculated.

If there is zero between imputation variance, e.g., if there are no missing data to impute, then the methods described in Step 2 will be applied to a single instance of the complete data set and it will not be necessary to combine estimated quantities in Step 3. Note that if the extent of missing data is considered sufficiently high, this analysis may be repeated with all missing microbiological responses at TOC, i.e. irrespective of the reason for missingness, and assessed using multiple imputation logistic regression. Prior to unblinding a review with GSK Microbiology will determine appropriate groupings of MICs (gepotidacin and ceftriaxone plus azithromycin) for the purposes of this analysis.

- 4) A tipping point analysis may be performed for the primary endpoint in the Micro-ITT population to assess the impact of failure imputation of missing data on the microbiological response at TOC. The scope of missing data will be consistent with the multiple imputation analyses, specifically, if the entire TOC Visit, microbiology samples were missed due to COVID-19 pandemic, then the missed value will be imputed under the MAR assumption. If the TOC microbiology sample was taken but a result is not available for the sample for any reason, then the missed value will also be imputed under the MAR assumption. All other missing data will be considered as a failure (i.e., non-responders) per the primary analysis. The tipping point analysis will vary assumptions on the proportion of participants achieving success in the two treatment groups. For each combination of assumed success rates in the two treatment groups, the number of additional participants achieving success among subjects with missing microbiological response will be imputed by drawing from a binomial distribution.
 - A grid of paired values will be established, ranging from 0 to 1 in steps of 0.025, establishing the assumed response rates for each treatment group in participants with missing microbiological response.
 - For each pair of assumed response rates corresponding to treatment group, $(\theta_{Gepotidacin}^{(i)}, \theta_{Ceftriaxone\ plus\ azithromycin}^{(j)})$, repeat the following steps 100 times:
 - Sample additional responders among participants with missing responses by drawing from a binomial distribution, using the assumed response rate assigned to each treatment group. Sampling will be completed separately by treatment,

$$r_{Gepotidacin}^a \sim \text{Binomial}(n_{Gepotidacin}^{miss}, \theta_{Gepotidacin}^{(i)})$$

$$r_{Ceftriaxone\ plus\ azithromycin}^a \sim \text{Binomial}(n_{Ceftriaxone\ plus\ azithromycin}^{miss}, \theta_{Ceftriaxone\ plus\ azithromycin}^{(j)})$$

- The proportion of success in each treatment group and the difference in the proportion of success between two treatment groups as well as the respective associated standard errors will be computed. Standard error of the risk difference estimate will be calculated using the MN method weighted on actual strata.

- Using Rubin's rules we will combine the estimated quantities (success rate in each treatment group, difference in proportions between two groups, and their standard errors). The calculations for pooled estimates will be implemented using SAS PROC MIANALYZE. 95% (Wald) CIs for the risk difference between the two treatment groups will be presented. The noninferiority conclusion will be drawn if lower limit of the 2-sided 95% confidence interval (CI) is above -10.0%. Testing for superiority may occur if noninferiority is achieved and one-sided p -values will be calculated.
- The process described above will be repeated for each pair of assumed response rates, $(\theta_{Gepotidacin}^{(i)}, \theta_{Ceftriaxone\ plus\ azithromycin}^{(j)})$.
 - Visual representations of treatment difference and noninferiority decisions will be produced using a colored heatmap illustrating the gradual change of treatment difference. Colored borders will be used to highlight the microbiological response rates that resulted in noninferiority.

If for a pair of assumed response rates there is zero between imputation variance, e.g., if there are no missing data to impute, then the methods described above for calculating the proportion of successes, risk difference and associated standard errors, will be applied to a single instance of the complete data set and it will not be necessary to combine estimated quantities across imputations. Note also that tipping point analysis may be repeated with a greater number of imputations (if necessary over a smaller, refined grid range), if tipping points are considered to be sensitive to the random number seed and/or number of imputations. Furthermore, if the extent of missing data is considered sufficiently high, tipping point analysis may be repeated, imputing all missing microbiological responses at TOC, irrespective of the reason for missingness, using random draws from a binomial distribution as described above.

- 5) Primary analysis is based on Micro-ITT population using CLSI breakpoints. The ceftriaxone MIC breakpoints for *N. gonorrhoeae* currently differ between CLSI and EUCAST, if isolates are identified with different interpretations applying the EUCAST breakpoints as compared to CLSI, a sensitivity analysis of primary endpoint will be produced on a population defined based on EUCAST breakpoints (Micro-ITT EU). Ceftriaxone susceptibility will be evaluated by applying EUCAST MIC breakpoints to results from ceftriaxone agar dilution testing. If an agar dilution value is not available for ceftriaxone, CLSI disk diffusion breakpoints will be applied to results from ceftriaxone disk diffusion testing. The number and percentage of participants with culture-confirmed bacterial eradication of NG from the body site will be summarized at the TOC visit by treatment group along with the 95% Exact (Clopper-Pearson) CIs. The adjusted estimates of the difference in microbiological success rate for the two treatment groups (gepotidacin – ceftriaxone plus azithromycin) will be calculated and summarized with 2-sided 95% CI based on a stratified analysis (pooled strata) using Miettinen and Nurminen (MN) method. Non-inferiority and superiority will be tested as stated in Section 2.4.

Note that if data warrant, this analysis may be repeated on the Micro-ITT and Micro-ITT EU populations, but excluding participants whose ceftriaxone susceptibility is determined by disk diffusion.

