- Collect a pretreatment urogenital swab specimen from all participants for Gram stain (males and females), bacterial culture, and in vitro susceptibility testing at Baseline. At TOC, a urogenital swab specimen will be collected for Gram stain, bacterial culture, and in vitro susceptibility testing. Note: **All** urogenital swab specimens will be processed for Gram stain testing following inoculation of the culture plates.
- Pretreatment rectal and pharyngeal swab specimens for bacterial culture and in vitro susceptibility testing will be obtained from participants who are willing to provide such specimens, regardless of known exposure. At TOC, swab specimens will be collected from pharyngeal and/or rectal sites that were collected at Baseline for bacterial culture and in vitro susceptibility testing. Note: **None** of the rectal or pharyngeal swab specimens will be processed for Gram stain testing.
- At Follow-up, pharyngeal swab specimens will be obtained for bacterial culture and in vitro susceptibility testing from participants who had a positive NAAT assay for pharyngeal NG at **both** Baseline and TOC. Results from the NAAT assay will be available to the study sites by the Follow-up Visit.
- See the laboratory manual for local versus central laboratory details and the number and type of specimens to collect.
- Pretreatment baseline urogenital specimens will be obtained from all participants for detection of NG, Mgen, and CT by NAAT. At Baseline, while detection of NG and CT by NAAT may be performed using the same urogenital sample, 2 separate samples must be obtained (1 for the local laboratory and 1 for the central laboratory).
- Urogenital specimens will be obtained from all participants for detection of NG and CT by NAAT at the TOC Visit.
- At Follow-up, a urogenital specimen will be collected for the detection of Mgen only by NAAT from participants who had a positive NAAT assay for Mgen at Baseline. Results from the NAAT assay will be available to the study sites by the Follow-up Visit.
- Pretreatment baseline pharyngeal and rectal specimens for detection of NG and CT by NAAT will be obtained from participants who are willing to provide such specimens, regardless of known exposure. At TOC, a specimen will be collected from pharyngeal and/or rectal sites that were collected at Baseline.

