5.4.1. Strata and Other Covariates

The list of covariates and other strata may be used in descriptive summaries and statistical analyses, some of which may also be used for subgroup analyses. Additional covariates and other strata of clinical interest may also be considered.

- If the number of participants is small within a category of a covariate or strata, then the covariate/strata categories may be further refined prior to unblinding the trial.
- If the category cannot be refined further, then the covariate may be included as a continuous measure.

Participants will be randomized to a treatment arm using stratification by sex and sexual orientation (men who have sex with men [MSM], men who have sex with women [MSW], or female) and age (<18 years, ≥18 to 65 years, or >65 years). The MSM category will include MSM and bisexual males (i.e., male participants who have sex with both males and females).

Summaries of participants for whom the randomized and actual strata differ, quantifying the number of participants whose strata differ between the primary analysis (adjusting for actual pooled strata) and the relevant sensitivity analysis (adjusting for pooled strata as randomized, Section 7.1.6.2) will be provided.

Randomized Stratification Factor	Randomized Stratification Level
Age Category	<18 years
	≥18 to 65 years
	>65 years
Sex and Sexual Orientation	Men who have sex with men (and females) (MSM)
	Men who have sex with women (MSW)
	Female

The stratification combinations are as follows:

Randomized Stratification Value	Randomized Stratification Description
1	<18 years, MSM
2	<18 years, MSW
3	<18 years, Female
4	≥18 to 65 years, MSM
5	≥18 to 65 years, MSW
6	≥18 to 65 years, Female
7	>65 years, MSM
8	>65 years, MSW
9	>65 years, Female

For primary analysis, stratification values (after combining the three age strata) are defined as follows:

Stratification Value	Stratification Description
1	MSM
2	MSW
3	Female

Other covariates considered in statistical analyses (for logistic regression used in multiple imputation):

Covariates
Randomized treatment
Sex and sexual orientation (MSM, MSW, or female)
Interaction term between treatment and MIC (gepotidacin or ceftriaxone plus azithromycin) for randomized treatment
Site (Sites with <10 participants in the Micro-ITT Population may be combined prior to unblinding)

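### The multiple-imputation sensitivity analysis fills in TOC cultures that were taken but gave no result without using the urogenital NG NAAT from the same visit

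*SAP*

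**What the plan says.** SAP Section 7.1.6.2, item 3, imputes two kinds of missing TOC response under missing at random: visits or samples missed because of COVID-19, and a second class described as "If the bacteriology sample was taken but a result is not available for the sample for any reason". All other missing responses stay failures.

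Step 1 is a logistic model. Its list begins "The variables used in the imputation model will include" and contains sex and sexual orientation, randomized treatment, "Interaction term between treatment and MIC (gepotidacin or ceftriaxone plus azithromycin) for randomized treatment", and site. Section 5.4.1 gives the same four covariates for the imputation regression. It also has a general sentence allowing further covariates of clinical interest, which names neither NAAT nor this model. Step 1 leaves out of the relevant model anyone with a missing predictor.

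On NAAT, the footnotes to Protocol Table 2 state: "Urogenital specimens will be obtained from all participants for detection of NG and CT by NAAT at the TOC Visit". SAP Table 7 (Appendix 1) shows the TOC urogenital NG test run in real time at the central laboratory. The SAP uses the result for exploratory endpoints (Section 7.3.1.5) and in the benefit/risk plot (Section 10). Nothing adds it to the imputation model or explains its absence.

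**The concern.** A participant whose culture was taken but not readable did attend TOC and should usually have a NAAT from that visit. Under Step 1, two such participants with the same arm, MIC group, stratum and site get the same imputed chance of success, even if one is NAAT-negative and the other NAAT-positive.

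Section 7.1.6.2 justifies missing at random by arguing that shipping, packing and labelling problems are unrelated to response, and it gives out-of-stability samples as an example. For those samples the SAP's own rules undercut the argument. Under note 3 to SAP Table 2 and Section 12.4.2, an out-of-stability culture that grows NG counts as persistence, while one that does not grow is set to unable to determine, because NG may be absent or may have died. Whether the result is missing therefore depends partly on the outcome. No listed covariate bears on absent versus no longer viable; a nucleic-acid test does.

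At stake is the credibility of an analysis that reports its own confidence interval and one-sided p-value.

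**Working it through.** **The plan's own figure.** Protocol Section 10.2.1 states about 91% power (200 per arm, 90% in both arms, margin -10%, one-sided 0.025). SE = sqrt(2 x 0.9 x 0.1 / 200) = 0.030, and 0.10/0.030 - 1.960 = 1.373, giving 91.5%. Enumerating the unstratified Miettinen-Nurminen test gives 90.0%. The figure is reproduced, and it does not depend on the imputation model.

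**Assumed inputs** (the documents give none of these):
- p = 0.95, success among participants with a readable culture.
- m = 10 or 20 taken-but-no-result cultures in one arm of 200.
- q = true success among those m.
- se = P(NAAT positive given persistence), 0.95 to 0.99.
- sp = P(NAAT negative given eradication), 0.60 to 0.95. The low end allows for residual nucleic acid.

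**Imputed probabilities.** By Bayes' rule, P(success | NAAT-) = p·sp / [p·sp + (1-p)(1-se)] and P(success | NAAT+) = p(1-sp) / [p(1-sp) + (1-p)se].
- se 0.95, sp 0.60: 0.57/0.5725 = 0.996 and 0.38/0.4275 = 0.889.
- se 0.99, sp 0.95: 0.9025/0.903 = 0.999 and 0.0475/0.097 = 0.490.

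The planned model gives about 0.95 to both groups.

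**Bias in the arm's success rate.** Without NAAT it is (m/200)(p - q). With NAAT it is (m/200)(p - q)(1 - R²), where R² = (se + sp - 1) x [P(success | NAAT-) - P(success | NAAT+)]. This gives R² = 0.55 x 0.107 = 0.06 at the weak end and 0.94 x 0.510 = 0.48 at the strong end.

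| m | q | Without NAAT (points) | With NAAT (points) |
|---|---|---|---|
| 10 | 0.95 | 0 | 0 |
| 10 | 0.85 | 0.50 | 0.26 to 0.47 |
| 10 | 0.70 | 1.25 | 0.65 to 1.18 |
| 20 | 0.85 | 1.00 | 0.52 to 0.94 |
| 20 | 0.70 | 2.50 | 1.30 to 2.35 |

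In these rows missingness depends on the culture itself, so NAAT reduces the bias without removing it. If data are missing at random given NAAT, adding it removes the bias. The planning rate of 90%, with non-returners counted as failures, leaves 0.10 x 200 = 20 failures per arm from all causes, so m = 20 is an extreme.

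**Direction for out-of-stability cultures.** Let d be the chance that NG which is present fails to grow in a late sample. Among the samples set to missing, success is p / [p + (1-p)d]. At d = 1 this is 0.95 (no bias), at d = 0.5 it is 0.95/0.975 = 0.974, and at d = 0 it is 1. The planned model then imputes too little success: for m = 10, by up to 10/200 x 0.05 = 0.25 points in that arm, and for m = 20, by up to 0.50. If delay itself is unrelated to response, this rule works against an arm with more late samples. Losses that fall more often on persistent infections work the other way, as in the table.

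**The case against.** Much of the opposing case stands.

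- **The primary result is not exposed.** The primary analysis counts every unreadable culture as a failure. A reader might infer that the noninferiority decision depends on this model; it does not.
- **The model is not empty of participant-level information.** Baseline MIC is individual data. In Phase II all three urogenital failures had a gepotidacin MIC of 1 µg/mL, and success was 100% at 0.5 or below (Protocol Sections 5.4 and 5.5). MIC says how likely cure was, however, not what was present at TOC.
- **An excess of NAAT-positives would not be invisible.** A reader might infer that it would be. TOC NAAT response is tabulated by arm (Table 2.329), missing data behind unable-to-determine outcomes are summarised (Table 2.341), and culture and NAAT results are listed by participant (Listings 601 to 603). None of these displays feeds the imputation.
- **The tipping-point grid covers success rates from 0 to 1 in each arm.** It therefore bounds anything NAAT could imply. The text says only that it may be performed, although Table 2.105 and Figure 2.104 are listed without condition. It also does not show which cells are plausible.
- **If losses are purely logistical, both models are unbiased** and NAAT adds only precision. That is a fair defence for mislabelled samples, less so for out-of-stability ones.
- **NAAT's predictive strength at TOC is unproven here.** Culture/NAAT concordance is planned at Baseline only (Table 1.307), residual nucleic acid weakens a positive result, and some courier or labelling failures could lose both specimens.

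**Conclusion.** The omission is real, and it appears in both places where the model is specified. For attenders with an unreadable culture, a same-site, same-visit result that is already collected is left out, and the out-of-stability rule makes missing at random given baseline covariates alone doubtful. Calling NAAT the most direct available information is a judgement: it tests the same organism, site and visit, while every listed predictor predates dosing.

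The consequence is confined to one sensitivity analysis. Under the assumptions above, the part of the bias that NAAT removes is at most 0.60 points with 10 such cultures in one arm (1.25 - 0.65) and at most 1.20 points in the extreme case of 20 (2.50 - 1.30), against a 10-point margin. In most cells it is well under one point. The true size depends on how many such cultures there are and on NAAT/culture agreement at TOC, neither of which the documents give. The change is worth making because it is cheap and makes the stated assumption more credible, not because the conclusion is in danger.

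**What to change.** Use two imputation models in Step 1.

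1. For participants who attended TOC and have a central-laboratory urogenital NG NAAT result, add that result (positive or negative) to the four existing predictors. Fit the model on participants with both an observed TOC culture and a NAAT result. Use an augmented or penalised likelihood, because few NAAT-negative participants will be culture-positive.
2. For COVID-missed visits, and for attenders without a NAAT result, keep the current model. Adding NAAT as an ordinary covariate would remove these participants under the missing-predictor rule. A separate not-available category would have very few observed cultures from which to estimate it.

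Specify in advance a check on whether the NAAT-culture relation differs by arm, since nucleic-acid clearance may itself differ by treatment. Document all of this before unblinding.

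The cost is a second imputation model and a little more programming. No new data are needed, and the estimand, primary analysis and sample size stay as they are.
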